6.4. Treatment Compliance

Treatment compliance will be directly observable by clinic staff, given that the study drugs are IV infusions. Pertinent data will be recorded in each subject's electronic case report form (eCRF).

6.5. Guidelines for Dose Modification

No dose modifications will be permitted in this study.

6.6. Prior and Concomitant Medications

All therapies received by subjects within 30 days prior to a subject's signing of the informed consent form (ICF) will be recorded as prior therapies.

All therapies used from the time the subject signs the ICF for study participation through the Follow-up Visits will be recorded as concomitant therapies. Concomitant therapies include all prescription, over-the-counter (OTC), and herbal remedies.

COVID-19 vaccine doses received prior to the study will be documented as prior medication, regardless of date of administration.

All prior and concomitant therapies will be recorded in the eCRF.

Changes to allowed (see Exclusion Criterion 11) SLE medications are permitted as long as they result in dose decrease and not increase.

6.7. Prohibited Therapies/Products

The following therapies and products are prohibited starting before randomization, as indicated below, and until the End of Treatment (EOT) Visit (Day 113).

- Topical corticosteroids and other topical immunosuppressive agents, including topical calcineurin inhibitors, whose prohibition starts 2 weeks prior to randomization (Day 1)
- Intralesional corticosteroids, IV, IM, and intra-articular corticosteroids, whose prohibition starts 4 weeks prior to randomization (Day 1)
- Cyclosporine, voclosporin, pimecrolimus, and sirolimus, whose prohibition starts 4 weeks prior to randomization (Day 1)
- Cyclophosphamide, whose prohibition starts 24 weeks prior to randomization (Day 1)
- IV Ig or plasmapheresis, whose prohibition starts 12 weeks prior to randomization (Day 1)
- All biologic agents, including anti-B-cell antibodies (eg, rituximab, ocrelizumab, and belimumab), other antibodies (eg, anifrolumab, adalimumab, and tocilizumab), Fc constructs (eg, abatacept and etanercept), cytokines, and live vaccines within 12 weeks prior to randomization (Day 1)

6.8. Permitted Therapies/Products

The use of acetaminophen of <2 g/d and 1% topical hydrocortisone for contact dermatitis are acceptable concomitant therapies at any time during the study. Stool softeners are allowed during the inpatient stay at the discretion of the investigator. Subjects may drink prune juice for constipation. The following medications are allowed: oral prednisone (or equivalent at a maximum of 20 mg/d); antimalarials at standard-of-care dose (maximum: hydroxychloroquine 400 mg/d, chloroquine 250 mg/d, quinacrine 100 mg/d); methotrexate (maximum 25 mg/wk); leflunomide (maximum 20 mg/d); mycophenolate (mycophenolate mofetil [MMF] maximum 3000 mg/d or mycophenolic acid sodium [MPS] maximum 2160 mg/d); azathioprine (maximum 200 mg/d); and tacrolimus (maximum 3 mg/d). These medications are allowed as long as they were initiated at least 12 weeks prior to randomization, have been stable for at least 4 weeks prior to randomization, and will remain stable for the duration of the study. Subjects who are not planning to continue these medications during the study must have discontinued them at least 4 weeks prior to randomization.

7. STUDY DRUG DISCONTINUATION AND DISCONTINUATION FROM THE STUDY

7.1. Discontinuation of Study Drug

The primary reason for the permanent discontinuation of DS-7011a treatment administration must be recorded. Reasons for treatment discontinuation include:

- Completed
- Death
- AE
- Withdrawal by Subject (**to discontinue study drug**) NOTE: in this section this is only withdrawal for treatment with study drug and is NOT the same thing as a complete withdrawal from the study. Discuss with the subject that they will remain in the study (ie, continue with study visits and assessments).
- Physician Decision
- Lost to Follow-up (see Section 7.4 for details on when a subject is considered Lost to Follow-up)
- Pregnancy
- Protocol Deviation
- Study Termination by Sponsor
- Other

After study drug is permanently discontinued for any reason other than death or lost to follow-up, the subject will be treated as clinically indicated by the investigator or referring physician.

The investigator must discuss with the subject that their decision to permanently discontinue the study drug means the subject still agrees to continue into the Follow-up Period for onsite or modified follow-up visits. Subjects will be followed at regularly scheduled intervals (see [Table 1.1](#)).

Procedures for Discontinuation from Study Drug

The subject should be instructed to contact the investigator or study site staff before or at the time study drug is discontinued.

If a subject is discontinued from the study drug:

- The reason(s) for discontinuation and the last dose date should be documented in the subject's medical record and eCRF.
- Due to an AE, the investigator will follow the subject until the AE has resolved or stabilized.

- An EOT evaluation should be performed as described in the Schedule of Events (SoE) (Table 1.1).
- A safety follow-up evaluation should be performed approximately 30 days after the last dose of study drug as described in the SoE (Table 1.1).

The investigator will complete and report the observations as thoroughly as possible up to the date of discontinuation, including the date of last dose. All procedures specified for the EOT visit will be conducted. See Table 1.1 for specific EOT procedures.

If a subject does not agree to continue to come to the study site, then a modified follow-up must be arranged to ensure the continued collection of endpoints and safety information. Options for modified follow-up are noted below.

Modified Follow-up Options

The following modified follow-up options can be offered to the subject who does not agree to study visits at the study site.

- Study personnel contacting the subject by telephone (may be quarterly, bi-annually, annually, or only at EOS)
- Study personnel contacting an alternative person (eg, family member, spouse, partner, legal representative, physician, or other healthcare provider)
- Study personnel accessing and reviewing the subject's medical information from alternative sources (eg, doctor's notes, hospital records)

Dates of the modified follow-up contact(s) should be recorded. See Section 7.2 for definition of withdrawal by subject from the study (ie, withdrawal of consent).

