2.3. Dose Selection

DS-7011a will be administered intravenously (IV) 3 times at the dose of 20 mg/kg q4w. This dose was selected based on the safety, tolerability, PK, and pharmacodynamic (PD) results of the DS-7011a FIH Phase 1a study, which was a single ascending-dose study in healthy subjects in which DS-7011a was explored at the doses of 0.1, 0.3, 1, 3, 10, and 20 mg/kg. In said Phase 1a study, the 20 mg/kg dose was found to be similarly safe and well tolerated to lower doses but maximally active pharmacodynamically and thus selected to explore DS-7011a in subjects with SLE in this Phase 1b/2 study. According to preliminary analysis, in said Phase 1a study, the 20 mg/kg dose resulted after a single IV administration in extensive ex vivo inhibition of IL-6 production, which was of early onset and lasting duration and was still 86% on average, more than 65% in each subject, and more than 95% in 40% of subjects after 4 weeks from the administration. The 20 mg/kg dose, which is 1/6 of the NOAEL human equivalent dose, also resulted in C_{max} (719 $\mu\text{g/mL}$) and area under the plasma concentration time curve up to infinity (AUC_{inf}) (8838 $\text{day} \cdot \mu\text{g/mL}$) that didn't exceed monkey NOAEL (400 mg/kg) C_{max} (14,700 $\mu\text{g/mL}$ [female] or 13,800 $\mu\text{g/mL}$ [male]) and AUC_{inf} (29,300 $\text{day} \cdot \mu\text{g/mL}$ [female] or 34,200 $\text{day} \cdot \mu\text{g/mL}$ [male]).

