8.8.1. Adverse Events

8.8.1.1. Methods to Detect Adverse Events

The definitions of an AE or SAE can be found in Section 10.4. AEs may be directly observed, reported spontaneously by the subject or by questioning the subject (or, when appropriate, by a caregiver, surrogate, or the subject's legally authorized representative) at each study visit. Subjects should be questioned in a general way, without asking about the occurrence of any specific symptoms. The investigator must assess all AEs to determine seriousness, severity, and causality. The investigator and any qualified designees are responsible for detecting, documenting, and recording events that meet the definition of an AE or SAE and remain responsible for following AEs that are serious, considered related to the study drug or study procedures, or that caused the subject to discontinue.

All clinical laboratory results, vital signs, and ECG results or findings should be appraised by the investigator to determine their clinical significance. Isolated abnormal laboratory results, vital sign findings, or ECG findings (ie, not part of a reported diagnosis) should be reported as AEs if they are symptomatic, lead to study drug discontinuation, require corrective treatment, or constitute an AE in the investigator's clinical judgment.

Medical conditions (including laboratory values/vital signs that are out of range) that were diagnosed or known to exist prior to informed consent will be recorded as part of medical history. COVID-19 assessments are detailed in Section 8.8.2.

8.8.1.2. Time Period for Collecting Adverse Events, including Adverse Events of Special Interest and Serious Adverse Events

For all randomized subjects, all AEs occurring after the subject signs the ICF and through the EOS Visit, whether observed by the investigator or reported by the subject, will be recorded as detailed in Section 10.1.6.2. All SAEs will be followed until resolution, stabilization, the event is otherwise explained, or the subject is lost to follow-up.

Medical conditions (including clinically significant laboratory values/vital signs that are out of range) that were diagnosed or known to exist prior to the consent date will be recorded as medical history, and not an AE. Exacerbation of a pre-existing medical condition or symptom, including increase in severity of the symptom will be recorded as an AE.

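### For subjects who stop study drug and decline site visits, the telephone frequencies in Section 7.1 do not fit a follow-up that ends on Day 169

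*Combined protocol and SAP*

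**What the plan says.** Section 7.1 keeps subjects who stop study drug in the study. The default is the Table 1.1 schedule: "Subjects will be followed at regularly scheduled intervals". An EOT evaluation is required, and if an AE caused the stop it is followed until it resolves or stabilizes. The section adds: "A safety follow-up evaluation should be performed approximately 30 days after the last dose of study drug as described in the SoE".

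If the subject will not come to the site, "a modified follow-up must be arranged to ensure the continued collection of endpoints and safety information". The options are introduced this way: "The following modified follow-up options can be offered to the subject who does not agree to study visits at the study site". The first is: "Study personnel contacting the subject by telephone (may be quarterly, bi-annually, annually, or only at EOS". The other two are contact with another person, such as a relative or physician, and review of medical records. Neither has a stated frequency.

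Other sections bear on this:
- Section 8.8.1.2 sets the AE collection period: "For all randomized subjects, all AEs occurring after the subject signs the ICF and through the EOS Visit".
- Section 4.1.2 and footnote a of Table 1.1 define a subject's EOS as the date of whichever visit or contact comes last. They schedule it for Day 169, by telephone unless blood is needed.
- Table 1.1 collects AEs at every visit. It has no column for an evaluation 30 days after the last dose.

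**The concern.** Modified follow-up is mandatory, and its stated purpose is to keep endpoint and safety data coming in. The frequencies listed for it would suit a study lasting years. In a follow-up of 24 weeks, some of them produce no call before the end.

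AEs, SAEs and AESIs are the primary endpoint. Section 9.4.2 keeps every dosed subject in the Safety Analysis Set. Sections 9.5.2 and 9.5.2.1 summarize TEAEs as incidence by treatment group and describe no adjustment for how often a subject was asked. A subject who is rarely asked therefore stays in the denominator and tends to count as event-free. The events most easily lost are non-serious ones, including mild respiratory infections, which are AESIs. Section 8.8.1.1 has subjects questioned in general terms only, which is a weak prompt for a minor infection some months back.

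**Working it through.** **Inputs.** Dosing on Days 1, 29 and 57 (Table 6.1). Scheduled end of follow-up on Day 169 ±3 days (Table 1.1). Screening of at most 28 days and a subject duration of about 28 weeks (Section 4.1.4). Up to 24 subjects randomized 2:1 (Section 9.2). Assumed intervals: quarterly 91 days, bi-annual (read as twice a year) 182 days, annual 365 days, all counted from the last dose.

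**1. The plan's own figure.** 28 + (169 − 1) = 196 days, and 196/7 = 28.0 weeks, as stated. The part after first dosing is 168/7 = 24.0 weeks.

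**2. Time left and first call.** Time left = 169 − day of last dose. First call = day of last dose + interval.

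| Last dose | Days left | Quarterly | Six-monthly | Annual | Later AE contacts in Table 1.1 |
|---|---|---|---|---|---|
| Day 1 | 168 | Day 92 | Day 183 | Day 366 | Days 2, 8, 29, 57, 85, 113, 169 |
| Day 29 | 140 | Day 120 | Day 211 | Day 394 | Days 57, 85, 113, 169 |
| Day 57 | 112 | Day 148 | Day 239 | Day 422 | Days 85, 113, 169 |

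No six-monthly or annual call falls by Day 169, or by Day 172 at the end of the visit window. Reading bi-annual as every two years, or starting the clock on a later stopping date, only moves the calls later. A second quarterly call would fall on the six-monthly day, so quarterly gives one interim call.

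**3. Contacts and recall.** The Day 169 contact is by telephone for all subjects, so declining site visits does not remove it. Six-monthly, annual and EOS-only each leave that one call, with recall of 168, 140 or 112 days from the last dose. Quarterly gives two calls. Recall is shorter if the subject was seen between the last dose and the refusal. If the 30-day evaluation takes place, the last gap is 168 − 30 = 138, 140 − 30 = 110 or 112 − 30 = 82 days. On the Table 1.1 schedule the longest gap is 169 − 113 = 56 days.

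**4. The 30-day evaluation.** Last dose + 30 gives Days 31, 59 and 87. These lie inside the windows of existing visits: Day 29 ±2 (27 to 31), Day 57 ±3 (54 to 60) and Day 85 ±3 (82 to 88).

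**5. Weight of one subject.** 24 × 2/3 = 16 and 24 × 1/3 = 8. One subject is 1/16 = 6.25% of the active arm or 1/8 = 12.5% of the placebo arm.

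**The case against.** The case on the other side is substantial, and much of it stands.

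- **Scope.** A reader might infer that everyone who stops early is poorly followed. Section 7.1 does not support that: only those who also decline site visits leave the Table 1.1 schedule.
- **No data at all.** A reader might infer that the two longest frequencies leave safety uncollected. Section 4.1.1 plans a telephone contact at Day 169 for everyone, and Section 8.8.1.2 requires AE collection through EOS, so one contact remains.
- **Longer than the study.** This holds for an annual interval against one subject's participation. It does not hold for a bi-annual one: 26 weeks is less than 28 and exceeds only the 24-week post-dose window. Neither exceeds the trial's 15 months.
- **30-day evaluation.** A reader might take it as missing from the schedule. It falls within existing visit windows, so this is a cross-reference to tidy up.
- **Continuing drug effect.** The Phase 1a inhibition figure in Section 2.3 ("was still 86% on average, more than 65% in each subject" four weeks after one dose) is a preliminary ex vivo result in healthy subjects. It does not measure AE risk after stopping.
- **AESI reporting.** The 24-hour rule runs from the investigator's awareness, so late recall does not breach it.
- **Other safeguards.** Record review, third-party contact, the EOT evaluation and follow-up of the AE that led to stopping all reduce the gap. They do not close it. The first two have no frequency and can miss a self-managed infection, no method is given for the EOT evaluation in someone who declines visits, and the last covers only the event that caused the stop.
- **Risk in the remedy.** Insisting on more calls could lead a reluctant subject to refuse telephone contact too. The fix has to allow for that.

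**Conclusion.** The point holds for subjects who stop drug and decline site visits. Two of the four listed telephone frequencies cannot produce a call before Day 169. With those two, or with EOS only, telephone ascertainment rests on one call with recall of 112 to 168 days; quarterly adds one call. That is at odds with the purpose Section 7.1 gives for modified follow-up. Because EOS is defined as the last contact, the EOS-only option also fixes no date.

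The consequence is possible under-ascertainment of non-serious AEs and AESIs in the primary safety summary. The documents give no estimate of how many subjects would be affected, so neither the size nor the direction of any difference between arms can be stated. The shares of 1/16 and 1/8 assume one such subject and full enrolment; replacements, which Section 8.5 permits, would make them smaller. The recall figures assume no contact between the last dose and Day 169. The change is worth making because it is cheap and bears on the primary endpoint.

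**What to change.** In Section 7.1:

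1. Replace the listed frequencies with telephone contact on each remaining Table 1.1 visit day, in the same windows, through Day 169. Each call collects AEs, AESIs and concomitant medications.
2. Allow less frequent contact for a subject who declines that schedule, and record this, so that the rule does not push anyone to withdraw.
3. State that EOS in this section means Day 169.
4. Map the 30-day evaluation to the scheduled visit whose window already contains it (Day 29, 57 or 85).

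For a subject whose last dose was on Day 1, the longest planned gap falls from 168 days under the EOS-only option to 56 days. The protocol already uses telephone AE collection at Day 169, so no new procedure is needed. The cost is amendment wording, a few extra calls and slightly more contact burden for these subjects. Remote collection of patient-reported scales is optional and not part of this correction.

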7.2. Subject Withdrawal/Discontinuation from the Study

Subjects may discontinue from the study for any of the following reasons:

- AE
- Death
- Consent withdrawal (this indicates that the subject withdraws consent and refuses to undergo any further study procedures)
- Lost to Follow-up (see Section 7.4 for details on when a subject is considered Lost to Follow-up)
- Study Termination by Sponsor
- Investigator decision
- Protocol deviation
- Pregnancy (see Section 8.8.1.9)
- Other

If the reason for study discontinuation is the death of the subject, the options for categorizing the primary cause of death are progressive disease or AE. If reason of death is unknown, every effort should be made to obtain the primary cause of death. Only 1 AE will be recognized as the primary cause of death.

Only subjects who refuse all of the following methods of follow-up will be considered to have withdrawn consent from study participation (ie, from the interventional portion and follow-up):

- Attendance at study visits per protocol
- Study personnel contacting the subject by telephone
- Study personnel contacting an alternative person
- Study personnel accessing and reviewing the subject's medical information from alternative sources

If the subject refuses all of the above methods of follow-up, the investigator should personally speak to the subject to ensure the subject understands all of the potential methods of follow-up. If the subject continues to refuse all potential methods of follow-up, the investigator will document this as a withdrawal of consent (from the interventional portion and follow-up).

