5.3. Screening Failures, Rescreening, and Subject Replacement

Rescreening is permitted after consultation with the Sponsor if a subject fails initial screening. Rescreening may occur only once. The subject identification number will remain the same at the time of rescreening. The initial screening information and the reason why the subject failed this screening will be recorded in EDC. If the subject also fails rescreening, rescreening information and reason for failure will similarly be recorded in EDC.

Subjects who discontinue the study may be replaced after consultation with the Sponsor.

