7.3. Withdrawal Procedures

In accordance with the Declaration of Helsinki and other applicable regulations, a subject has the right to withdraw from the study at any time and for any reason without prejudice to his or her future medical care by the study physician or at the study site.

If a subject withdraws from the study, she/he will be required to have early termination (ET) study procedures performed (refer to [Table 1.1](#)). All subjects who are withdrawn from the study should complete the protocol-specified withdrawal procedures.

If a subject is withdrawn from the study, the investigator will complete and report the observations as thoroughly as possible up to the date of withdrawal, including the date of treatment and the reason for withdrawal.

If the subject is withdrawn due to an AE, the investigator will follow the subject until the AE has resolved or stabilized.

In addition:

- Disclosure of future information is also withdrawn; the Sponsor may retain and continue to use any data collected before such a withdrawal of consent;
- The subject may request destruction of any samples taken and not tested, and the investigator must document this in the site study records;
- Study site personnel may use local, regional, and national public records (in accordance with local law) to monitor vital status.

See SoE ([Table 1.1](#)) for data to be collected at the time of study discontinuation and follow-up and for any further evaluations that need to be completed.

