9.2. Sample Size Determination

The study will enroll up to 24 subjects with SLE in 2 parallel arms randomized to receive 2:1 DS-7011a or placebo. Tentatively, 9 of these 24 subjects will be of African descent. Also, tentatively, 9 of these 24 subjects will be positive for anti-Sm and/or anti-RNP autoantibodies.

The sample size selected is not based on statistical power considerations. The number of subjects in each arm is considered sufficient to achieve the objectives of this study. Initial evidence of DS-7011a efficacy will be inferred by the impact DS-7011a shows on clinical endpoints, mainly CLASI-A, and several mechanistic endpoints. This impact will be evinced by comparing endpoint values between DS-7011a-treated and placebo-treated subjects and between pretreatment (baseline) and post-treatment time points. Concomitant and consistent impact on multiple endpoints will be initial evidence of efficacy, especially if this impact is of large extent. DS-7011a extent of impact will be compared to that reported for antibodies approved (belimumab and anifrolumab) or in late phase of development (BIIB059) for the treatment of SLE². The result of this comparison will inform a DS-7011a “go/no-go” decision to further development.

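### Sections 7.1 and 7.2 treat the same four events both as reasons to stop drug and stay in follow-up and as reasons to leave the study, and no rule limits the second route

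*Combined protocol and SAP*

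**What the plan says.** Section 7.1 gives the reasons for permanently stopping study drug. They include AE, physician decision, pregnancy and protocol deviation. The investigator must explain to the subject that "their decision to permanently discontinue the study drug means the subject still agrees to continue into the Follow-up Period". The section adds that "Subjects will be followed at regularly scheduled intervals", with reference to Table 1.1. For a subject who will not come to the site, modified follow-up (telephone, another contact person, medical records) has to be arranged.

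Section 7.2 concerns leaving the study itself: "Subjects may discontinue from the study for any of the following reasons". Its list contains AE, investigator decision, protocol deviation, pregnancy and Other, next to death, consent withdrawal, loss to follow-up and termination by the Sponsor. The test that a subject must refuse all four methods of follow-up is attached to consent withdrawal only.

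Section 7.3 requires early termination procedures on withdrawal and says: "If the subject is withdrawn due to an AE, the investigator will follow the subject until the AE has resolved or stabilized". Section 8.8.1.2 has SAEs followed to resolution or stabilization, and Section 8.8.1.9 has pregnancies followed to their conclusion. Section 6.3.2 says that a subject unblinded in an emergency ends both treatment and study participation.

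On replacement, Section 5.3 states: "Subjects who discontinue the study may be replaced after consultation with the Sponsor". Section 8.5 is worded similarly, for subjects who withdraw from the study.

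**The concern.** The four events do not in themselves take away the subject's consent to be observed, and Section 7.1 treats them accordingly. Section 7.2 lets a site end participation for the same events while the subject is still willing to be seen. Two sites could handle one event differently and both comply with the protocol.

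Safety is the primary objective. If leaving the study is tied to an adverse event or to an investigator's decision, the length of observation depends on the outcome being measured. Section 9.5.2.1 plans incidence of treatment-emergent events by treatment group and describes no adjustment for unequal follow-up. New events after an exit would then go uncounted while the subject remains in the denominator. The missing CLASI-A, PK/PD and ADA values would be related to tolerability, and the go/no-go comparison in Section 9.2 draws on the efficacy and mechanistic data.

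**Working it through.** The plan states no figure that depends on this point, so the check is a comparison of the texts followed by simple arithmetic.

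**1. The four events side by side**

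| Event | Section 7.1 | Section 7.2 | Event-specific follow-up after an exit |
|---|---|---|---|
| AE | Drug stops, follow-up continues | May leave study | Causal AE (7.3); SAEs (8.8.1.2) |
| Physician/investigator decision | Same | May leave study | None specific; SAEs (8.8.1.2) |
| Pregnancy | Same | May leave study | Pregnancy to outcome (8.8.1.9); SAEs (8.8.1.2) |
| Protocol deviation | Same | May leave study | None specific; SAEs (8.8.1.2) |

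Early termination procedures (7.3) apply to all four. Section 7.3 refers to Table 1.1 for them, but the table shows EOT and EOS columns and none labelled early termination.

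**2. What an exit closes**

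- AEs are collected through the EOS Visit (8.8.1.2), and EOS is defined as the subject's last visit or contact (4.1.2). An early exit therefore moves the end of AE and AESI collection forward.
- Scheduled efficacy, PK and PD assessments run to Day 113 (Table 1.1).
- The Day 169 ADA sample is taken only from subjects positive on Day 113 (8.7.3). A subject who has left before Day 113 does not reach that trigger.

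**3. Upper bound on scheduled time lost by one subject**

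Planned time from Day 1 is 113 − 1 = 112 days to the EOT Visit and 169 − 1 = 168 days to the EOS Visit. For an exit on day d, the loss is (113 − d)/112 and (169 − d)/168.

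| Exit day | To Day 113 | To Day 169 |
|---|---|---|
| 29 | 84/112 = 75% | 140/168 = 83% |
| 57 | 56/112 = 50% | 112/168 = 67% |
| 85 | 28/112 = 25% | 84/168 = 50% |

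An exit on Day 29 misses four scheduled contacts: Days 57, 85, 113 and 169. These are upper bounds, because they assume that nothing is collected after the exit day.

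**4. Weight of one subject**

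Section 9.2: "The study will enroll up to 24 subjects with SLE in 2 parallel arms randomized to receive 2:1 DS-7011a or placebo". That gives 24 × 2/3 = 16 on DS-7011a and 24 × 1/3 = 8 on placebo. One exit is 1/16 = 6.3% of the active arm or 1/8 = 12.5% of placebo.

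**5. Chance of at least one such exit**

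No exit rate is stated. For assumed rates p of 5%, 10% and 20%, the chance of at least one exit among 16 is 1 − (1 − p)^16 = 56%, 81% and 97%.

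**6. Analysis sets**

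The Safety set (9.4.2) and the mITT set (9.4.4) require only that a subject was dosed (and, for mITT, randomized). A dosed subject who leaves stays in both, and the event that led to the exit is still counted.

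**The case against.** The strongest defence is that the two sections do different jobs. Section 7.1 sets retention as the default after drug is stopped, and Section 7.2 is permissive. That stands: the loss is possible, not certain. What is missing is a limit on the exception, since the refusal test does not reach the four events or Other.

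A reader might infer that observation stops altogether. It does not, given the early termination procedures and the continued follow-up of the causal AE, SAEs and pregnancies. The EOT evaluation and the safety evaluation about 30 days after the last dose in Section 7.1 arguably apply as well, because leaving the study also ends study drug. The gap is in scheduled assessments and in new events after the last contact.

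A reader might also infer that replacement removes subjects with problems or by itself lowers the AE incidence. The documents do not support this. Replacement deletes no dosed subject from the Safety or mITT set, it needs consultation with the Sponsor, and a subject who only stops drug is already outside the wording of Sections 5.3 and 8.5. Any understatement would come from the shortened observation.

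The study is also descriptive. Section 9.1 disclaims hypothesis testing, and Section 9.2 says: "The sample size selected is not based on statistical power considerations". Section 9.5 leaves missing data to the SAP, so it cannot be said that the analysis ignores the problem. Both remarks lower the stakes, but neither recovers observations that were never made.

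**Conclusion.** The point holds as an unresolved overlap between Sections 7.1 and 7.2. A site that follows Section 7.2 as written can end follow-up of a willing subject because of an AE, an investigator decision, a pregnancy, a protocol deviation or Other. The data then lost are scheduled efficacy, PK/PD and ADA assessments and new AEs and AESIs. This loss can be informative for the primary safety objective.

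The size rests on the assumption of no data after the exit and is therefore a maximum. How many subjects would be affected cannot be derived from the documents. In arms of about 16 and 8, even one exit is visible in the percentages. The point is worth an amendment, but it does not call the design into question.

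**What to change.** Reconcile Sections 7.1, 7.2 and 6.3.2 so that reasons for stopping study drug are kept apart from reasons for ending follow-up.

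- In Section 7.2, state that AE, pregnancy, protocol deviation, investigator decision and Other do not by themselves end follow-up. Scheduled or modified assessments continue through Day 169 unless the subject dies, withdraws consent or is lost to follow-up, or the Sponsor ends the study.
- Reconcile this with the emergency-unblinding sentence in Section 6.3.2, which at present ends study participation and would otherwise conflict with the revised list.

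Sections 5.3 and 8.5 need no new exclusion for subjects who only stop drug. Which events lead to stopping study drug is unchanged.

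The cost is amendment wording, revised disposition codes in the eCRF and a few additional visits or calls. A subject who wishes to leave can still withdraw consent.
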